4.2.3 EXPLORATORY ENDPOINTS

1) Early diastolic myocardial velocity (Em): measured 30 minutes before HD end during 7th treatment in the first phase of each treatment type (once during conventional and once during UF profiled treatment); calculated as the average of early diastolic velocities recorded at the medial and lateral mitral annulus, see Appendix A for TTE protocol

2) Tricuspid annulus systolic excursion velocity (S_t): measured 30 minutes before HD end during 7th treatment in the first phase of each treatment type (once during conventional and once during UF profiled treatment); measured as the distance of tricuspid annular movement between end-diastole to end-systole (cm), see Appendix A for TTE protocol

3) Blood volume monitor slope (by hour): measured during the 1st (last) HD treatment of each week, hour-by-hour basis; defined as change in blood volume (%) on an hourly basis

4) Blood volume monitor slope (by treatment): measured during the 1st (last) HD treatment of each week, from start to end of HD treatment; defined as change in blood volume (%) over the entire HD treatment

5) Plasma refill: measured 10 minutes before HD end during 7th treatment of each phase; defined as the percentage increase in hematocrit

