2.2 RATIONALE

UF profiling, the practice of varying UF rates to maximize fluid removal during periods of greatest hydration and plasma oncotic pressure, is one treatment modification that may reduce UF-related harm without necessitating reduction in interdialytic fluid intake or longer HD treatments. While UF profiling has been available for decades, it has not been adequately studied independently of sodium profiling. Sodium profiling uses a higher dialysate sodium concentration to increase plasma osmolality. While sodium profiling (\pm UF profiling) often reduces hypotension, it disadvantageously sodium-loads the patient. The resultant positive sodium balance leads to increased thirst, weight gain, and interdialytic hypertension. Sodium profiling has been dismissed as a viable treatment option due to these disadvantageous side effects. Alternatively, UF profiling may reduce UF-related hemodynamic instability and associated cardiovascular consequences without altering sodium balance. Hypotensive episodes occur when UF rates exceed plasma refill rates. UF profiling allows for lower UF rates later in the HD treatment when plasma refill rates are the slowest and hemodynamic instability risk the highest. Thus, UF profiling has the potential to improve hemodynamic stability without untoward sodium gains.

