10.4.11 EXPLORATORY ANALYSES

Comparisons of values for the continuous exploratory endpoints of early diastolic myocardial velocity change, tricuspid annulus systolic excursion velocity change, blood volume monitor slope change and plasma refill change will be performed using ANOVA or non-parametric methods depending on data type.

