Depending on the type of various endpoints, we propose to perform the following tests to test the difference between UF profile and conventional treatment.

- **Binary Outcomes**
 - We will perform repeated measure logistic regression by regressing the binary outcome on the treatment indicator and test if the coefficient before the treatment indicator is significant. Each subject will have a random intercept. The model is given by
$$\text{logit}(\text{outcome}) \sim 1 + \text{treatment} + (1|ID)$$
- **Continuous Outcomes**
 - We will perform repeated measure linear regression by regressing the continuous outcome (percentage outcome will be log-transformed) on the treatment indicator and test if the coefficient before the treatment indicator is significant. Each subject will have a random intercept. The model is given by
$$\text{outcome} \sim 1 + \text{treatment} + (1|ID)$$
- **Categorical Outcomes**
 - We will perform repeated measure multinomial regression by regressing the categorical outcome on the treatment indicator and test if the coefficient before the treatment indicator is significant. Each subject will have a random intercept. The model is given by
$$\text{multi-logit}(\text{outcome}) \sim 1 + \text{treatment} + (1|ID)$$

Quality Check

For patients who dropped out during the study, normalize endpoints to the same scale as the other patients, depending on the type of endpoints.

Sensitivity Analyses

1. Exclude participants who dropped out from all analyses.
2. Exclude participants who had endpoint data drawn "off-schedule" (troponin T, symptoms, etc.) from individual endpoint analyses.
3. Exclude participants who had an abnormality with their troponin T blood draw from troponin T-related analyses.
4. Test for difference by order of randomization (UF profiling --> conventional --> UF profiling --> conventional) vs. (conventional --> UF profiling --> conventional --> UF profiling)
5. Test for difference by clinic (site 1 vs. site 2)

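### The SAP does not say how the hourly blood volume values are modelled; if they are pooled in its single-coefficient model, the early-versus-late pattern cannot be seen

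*Combined protocol and SAP*

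**What the plan says.** Protocol 4.2.3 separates two blood volume slopes. Endpoint 3 reads "Blood volume monitor slope (by hour): measured during the 1st (last) HD treatment of each week, hour-by-hour basis; defined as change in blood volume", in percent for each hour. The by-treatment slope (endpoint 4) is "defined as change in blood volume (%) over the entire HD treatment". Endpoint 3 therefore gives several values per session and endpoint 4 gives one.

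The SAP (Primary Analysis, Continuous Outcomes) has one model, outcome ~ 1 + treatment + (1|ID). The instruction is to "test if the coefficient before the treatment indicator is significant. Each subject will have a random intercept". It also sets a scale rule: "regressing the continuous outcome (percentage outcome will be log-transformed) on the treatment indicator". The SAP does not name either blood volume endpoint.

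Protocol 10.4.11 says only that comparisons of "blood volume monitor slope change and plasma refill change will be performed using ANOVA or non-parametric methods depending on data type". Protocol 10.4.1 describes repeated-measures ANOVA for comparing HD treatments. Neither section lists hour as a factor.

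The intervention (protocol 4.1 and 6.1.1) is a UF rate that starts at 1.33 times the constant rate and falls linearly. In both arms total UF volume is set by the treating nephrologist (7.1.1, 7.1.2). The rationale in 2.2 is that "UF profiling allows for lower UF rates later in the HD treatment when plasma refill rates are the slowest".

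**The concern.** Profiling redistributes fluid removal within a session and, by design, does not change the total. The expected signature in blood volume is a pattern over time: a steeper fall early and a flatter course late. A model with one treatment coefficient and no hour term cannot express that pattern. If the hourly values are stacked in it, the early and late differences are averaged together.

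What is at stake is the information in endpoint 3. Pooled, its treatment contrast is essentially that of endpoint 4 on another scale, and the hour-to-hour course that both arms share stays in the residual.

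**Working it through.** The plan gives no effect size, SD or power for the blood volume endpoints, so there is no stated figure to reproduce. From the documents: the 1.33 starting multiplier, the linear decline, 30 patients, two phases per arm, nine thrice-weekly treatments per phase and two-sided alpha 0.05. Assumed: 4-hour sessions, one monitored session per week (three per phase), the SDs, and the blood volume response.

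**1. Profile by hour.** With equal total volume the rate must average 1, so it ends at 2 − 1.33 = 0.67. The rate is 1.33 − 0.66·t/4. Its hourly means are 1.2475, 1.0825, 0.9175 and 0.7525, and their mean is 1.000. For 3 hours they are 1.22, 1.00 and 0.78. For 5 hours they run from 1.264 to 0.736. The early excess and late deficit in UF offset exactly.

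**2. Identity.** Hourly changes within a session sum to the session change. With H complete, equal hours on the raw scale, pooled coefficient = mean of the hourly effects = (endpoint 4 effect)/H. In a simulation (30 patients, 6 sessions per patient per arm, 4 hours, assumed hourly effects −1, −0.35, +0.35 and +1 points):
- SAP model on stacked hours: −0.025 (SE 0.118, p = 0.83).
- Same model on session totals, divided by 4: −0.025 (SE 0.100). The larger SE for stacked hours reflects the unmodelled hour pattern.
- Model with treatment-by-hour: −1.12, −0.28, +0.27 and +1.04; interaction chi-square 87.2 on 3 df.

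**3. Where the identity is not exact.** With about 20% of last-hour values missing, the pooled coefficient was −0.087, against −0.117 for session change per observed hour. In a 3.5-hour session with the last half hour counted as a full row, the mean multiplier is 0.965, not 1. On the log of the hourly decline, the mean log ratio over 4 hours is −0.0175 (ratio 0.983): still near cancellation, but no longer session change divided by hours. The log is undefined for a negative change as the endpoint is defined. Reversing the sign moves the problem to any hour in which blood volume rises.

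**4. Power without refill.** Assume change proportional to UF rate and −2.5% per hour in control. The hourly effects are −0.62, −0.21, +0.21 and +0.62, with sum of squares 0.851, and the pooled effect is 0. Sessions per arm: 30 × 2 × 3 = 180. The variance of one hourly difference is 2·SD²/180, and the noncentrality is 0.851 divided by that variance.

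| Residual SD | Noncentrality | Power, 3-df treatment-by-hour test |
|---|---|---|
| 2 | 19.1 | 0.97 |
| 3 | 8.5 | 0.68 |
| 4 | 4.8 | 0.42 |

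The pooled test has power equal to alpha here, because its effect is zero by construction.

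**5. Power with refill.** Let the deficit D follow dD/dt = UF(t) − k·D, with 3 L removed over 4 hours and 5 L blood volume. For k = 1.5 per hour the hourly differences are −1.77, +0.89, +1.48 and +1.61. Their sum is +2.21 and the pooled coefficient is 2.21/4 = +0.55. Its SE is SD·√(2/720), since 180 × 4 = 720 rows per arm. Power is about 1.00, 0.94 and 0.75 for SD 2, 3 and 4. Over k = 0.5 to 2.0 the ranges are 0.99–1.00, 0.84–0.99 and 0.60–0.89. Throughout, the first-hour difference is negative and the last-hour difference positive. These power figures treat residuals as independent, so they are illustrative.

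**The case against.** The strongest objection is that pooling is inferred. The SAP never says that hourly values are stacked. Fitting its model separately to each hour would obey it to the letter, and nothing would cancel. Repeated-measures ANOVA could also carry hour as a within-session factor. This stands: the documents are silent rather than wrong. But stacking is the natural reading of one model with one tested coefficient, 10.4.1 frames the ANOVA as a comparison between HD treatments, and hour-specific fits are not specified either.

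A reader might infer four stronger things that the documents do not support:

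- *That endpoint 3 always reduces exactly to endpoint 4.* This needs untransformed values and complete, equal hours, whereas the SAP log-transforms percentage outcomes.
- *That the pooled test has almost no power.* This holds only under proportionality to UF rate. The protocol's own rationale rests on refill, and step 5 shows that the pooled test can then be well powered.
- *That a null result would be taken as no effect.* Protocol 10.4.1 says non-significant tests will be reported as inconclusive and that estimates and intervals will be weighed.
- *That the time pattern is the only reason for an hourly endpoint.* No section gives a reason, and the definition could also be read as a rate per hour.

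**Conclusion.** The concern holds as a specification gap. The model has no hour or treatment-by-hour term, and nothing says how several hourly values per session are to be handled. If they are pooled, the coefficient averages over hours and cannot show the early-versus-late pattern that the declining profile and section 2.2 predict. The offset is complete if blood volume follows UF rate proportionally and partial with refill. Any power that the pooled test keeps is power for the endpoint 4 contrast.

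The multipliers follow from the protocol's 1.33 once equal volume and a session length are assumed. The blood volume effects, SDs and refill rates are assumptions, so the power figures show direction and range only. The importance is low: this is one exploratory endpoint in a pilot, and the primary and secondary conclusions do not depend on it.

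**What to change.** In the SAP, for blood volume slope by hour only, specify outcome ~ treatment * hour + (1|ID) + (1|ID:session), with hour categorical. State that the outcome is analysed in untransformed percentage points. Report the treatment difference with a 95% CI for each hour, and make the treatment-by-hour test the test for endpoint 3. Say how part-hours and missing hours are treated. Keep the single-coefficient model for endpoint 4; its whole-session change is also signed, so the statement of scale should cover it too.

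The cost is a few lines of SAP text and one extra model on data already being collected. The drawback is a test with several degrees of freedom (3 for a 4-hour session) instead of 1.

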6.1.2 DURATION OF THERAPY

Patients will undergo 9 treatments during each phase for a total of 18 conventional HD treatments and 18 UF profiled treatments. Patients will undergo 3 wash-out HD treatments between phases. There will be a total of 45 study treatments (36 study treatments and 9 washout treatments). The baseline study visit will involve a history and physical and baseline transthoracic echocardiography study. The entire study duration for each individual is 16 weeks (15 treatments and 1 baseline study visit).

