7 STUDY PROCEDURES AND SCHEDULE

7.1 STUDY PROCEDURES/EVALUATIONS

7.1.1 STUDY SPECIFIC PROCEDURES

UF profiled HD treatments (intervention): The study treatments will be administered at routine, scheduled outpatient thrice-weekly HD clinic visits. Dialysis clinic nursing staff will select UF profile 2 on the dialysis machine at the start of each UF profiled treatment. Clinic nursing staff have experience using UF profiling as it is a standard HD machine setting. Dialysate composition and HD medications will be per baseline prescription determined by the treating nephrologist. Total UF volume and target weight will be determined by the treating nephrologist.

Medical history: At baseline, the participant’s medical history will be taken from the electronic medical record and confirmed verbally with the patient. The medical history will include a review of co-morbid conditions, medications

and performance of a physical examination (Vital signs- BP, heart rate, respiratory rate, weight, height; systems- cardiovascular, pulmonary, neurological)

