7.2.2 OTHER ASSAYS OR PROCEDURES

TTE: Patients will undergo intradialytic TTE at baseline (within 6 weeks prior to study start) and 30 minutes prior to HD end ("peak stress") during treatment 7 of the first phase of each treatment type (once during conventional and once during UF profiled treatment) (1 TTE during UF profiled HD and 1 during control HD). Study TTEs will be performed by a trained sonographer with a Philips CX50 ultrasound system (Philips North America).

Blood volume monitoring: Blood volume monitoring will be performed continuously throughout each study treatment via a Crit-line™ (standard-of-care non-invasive relative blood volume monitoring tool used as part of standard dialysis treatments).

Plasma refill test: Using the blood volume monitor, a plasma refill test will be performed 10 minutes before HD end during the 7th treatment of each phase. At the start of the treatment, UF time will be set 10 minutes less than treatment time. When the dialysis UF ends, study staff will document the hematocrit (%) from the blood volume monitor, and when the treatment ends, document the blood volume monitor hematocrit (%) again. Plasma refill tests are part of the blood volume monitoring protocols at the selected units and are familiar to staff.

Patient acceptance: At the end of the 9th study treatment of each phase, study staff will ask the participant the following question: "If recommended by your physician, would you be willing to adopt the HD prescription you have received during the last 9 treatments?"

Symptom assessment: At the conclusion of the 1st study treatment each week, study staff will ask patients to complete a symptom questionnaire (Appendix B).

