7.3.7 SCHEDULE OF EVENTS TABLE

Procedures	Baseline (6 week prior to study start)	Every study HD treatment	Before and after 7 th HD treatment of each phase	During 7 th HD treatment of each phase (twice per treatment type)	During 7 th HD treatment in the first phase of each treatment type (once per treatment type)	After 9 th HD treatment of each phase	After 1st HD treatment of each week (3x/phase)
Baseline laboratory testing	X						
Baseline history and physical	X						
Pregnancy status inquiry	X						
BP monitoring	X	X					
Weight monitoring	X	X					
Blood volume monitoring	X					X	
Troponin T laboratory testing			X				
TTE	X				X		
Plasma refill test	X			X			
Patient acceptance assessment						X	
Symptoms assessment						X	

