11 SOURCE DOCUMENTS AND ACCESS TO SOURCE DATA/DOCUMENTS

Each participating site will maintain appropriate medical and research records for this trial, in compliance with ICH E6 and regulatory and institutional requirements for the protection of confidentiality of participants. As part of participating in a NIH IC-sponsored study, each site will permit authorized representatives of the NIH IC and regulatory agencies to examine (and when permitted by applicable law, to copy) clinical records for the purposes of quality assurance reviews, audits, and evaluation of the study safety, progress and data validity. Study staff will have access to study records.

Data (blood pressures, weights, dialysis treatment data) will be extracted from electronic medical records and stored in password-protected Excel flowsheets housed on a secure Department of Medicine server. Blood

volume monitor, treatment preference, and symptoms will be recorded on study data collection forms. TTE data will be downloaded from the TTE machine to secure Department of Medicine Servers, per standard protocols. All electronic information will be stored on a password-protected UNC server (with secure, password and firewall-protected Department of Medicine server back-up) and accessed via a UNC password-protected computer and will be identifiably by study identification number only. Information linking the study identification number to the patient will be kept in a separate, password-protected database on the server. Study charts will be maintained in a locked room of the dialysis clinic. Study charts will be identified by study IDs. Signed consent forms will be kept in a locked filing cabinet in the PI's locked office. Initial paper records of study HD treatment data, patient preferences and symptoms will be stored in the study chart and, after study completion, will be transferred to a locked filing cabinet in the locked office of the PI. Paper records will be destroyed (shredded and disposed in locked, shred bins) after verification of electronic data entry. Only the PI and research assistant will have access to patient information with patient identifiers.

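### Both exploratory blood volume slope endpoints leave open which weekly session is meant, use 3 (or at most 6) of the 9 monitored sessions per phase, and are analysed without a session-of-week term

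*Combined protocol and SAP*

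**What the plan says.** Protocol section 4.2.3 lists two blood volume slope endpoints. The hourly one is "measured during the 1st (last) HD treatment of each week, hour-by-hour basis"; the whole-treatment one is "measured during the 1st (last) HD treatment of each week, from start to end of HD treatment". Both give first and last together and do not say how they relate.

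Other sections bear on which sessions are available:

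- Section 7.2.2: "Blood volume monitoring will be performed continuously throughout each study treatment".
- Section 7.3.7, schedule of events: the blood volume row is marked at baseline and in one later column, but not in the column for every study treatment. The table also has a weekly column headed "After 1st HD treatment of each week (3x/phase)".
- Section 11: blood "volume monitor, treatment preference, and symptoms will be recorded on study data collection forms", with no statement of which treatments those forms cover.
- Sections 6.1.2 and 7.1.1: "Patients will undergo 9 treatments during each phase for a total of 18 conventional HD treatments and 18 UF profiled treatments", given at "routine, scheduled outpatient thrice-weekly HD clinic visits".

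On analysis, section 10.4.11 plans ANOVA or a non-parametric method for the slopes. The SAP's model for continuous outcomes has a treatment indicator and a random intercept per participant. Neither says which sessions enter, and neither has a term for position in the week.

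**The concern.** Three sessions cannot divide seven days evenly, so one session a week follows a longer gap than the others. The documents do not give weekdays; on the usual calendar that session is the first. First and last sessions can therefore differ in the fluid to be removed, and blood volume slope is likely to respond to that. If both kinds of session enter the analysis without a term for position, the difference between them goes into the residual. If only one kind is used, nothing written beforehand says which, so the choice could be made after the data have been seen.

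There are two practical consequences:

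- Section 5.3 says missed treatments are not made up. With three sessions per phase, one miss loses a third of that phase's slope data; with nine, it loses a ninth.
- The SAP's second sensitivity analysis excludes participants whose endpoint data were taken off schedule. That rule cannot be applied to blood volume slope until its schedule is defined.

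**Working it through.** **Counts.** The plan's own totals reproduce: 4 phases × 9 = 36 study treatments, 3 washouts × 3 = 9, and 36 + 9 = 45 (section 6.1.2). At three treatments a week, 9 / 3 = 3 weeks per phase, which agrees with three first-of-week sessions per phase in the schedule header. Any nine consecutive thrice-weekly sessions contain each weekly position exactly three times, whatever day the phase starts.

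| Reading of the session rule | Per phase | Per participant | 30 completers | Share of monitored sessions outside the definition |
|---|---|---|---|---|
| One session a week | 3 of 9 | 12 of 36 | 360 of 1,080 | 6/9 = 67% |
| Both first and last | 6 of 9 | 24 of 36 | 720 of 1,080 | 3/9 = 33% |
| All monitored sessions | 9 of 9 | 36 of 36 | 1,080 of 1,080 | 0% |

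**Alignment of phases.** A phase plus its washout is 9 + 3 = 12 treatments, and 12 / 3 = 4 whole weeks. Since missed treatments are not made up, each phase starts at the same weekly position as the one before. A session rule applied consistently therefore gives both arms the same planned mix of sessions.

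**Precision of a phase mean (illustration).** The documents give no variance or correlation for these endpoints, so the within-phase correlation ρ is assumed. The variance of a mean of m sessions is proportional to ρ + (1 − ρ)/m. The standard error (SE) ratio for 9 against 3 sessions is

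√{[ρ + (1 − ρ)/9] / [ρ + (1 − ρ)/3]}

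- ρ = 0: √(0.1111/0.3333) = 0.577, a 42% reduction
- ρ = 0.1: √(0.2000/0.4000) = 0.707, a 29% reduction
- ρ = 0.3: √(0.3778/0.5333) = 0.842, a 16% reduction
- ρ = 0.6: √(0.6444/0.7333) = 0.937, a 6% reduction

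**Precision per arm (illustration).** The crossover estimates a within-participant contrast, not a phase mean. Let r be the assumed share of variance in an arm mean that averaging over sessions does not reduce. With f(m) = r + (1 − r)/m, using 6 rather than 18 sessions per arm multiplies the SE by √[f(6)/f(18)]. This is 1.73 at r = 0, 1.29 at r = 0.1, 1.17 at r = 0.2 and 1.05 at r = 0.5. Using 12 rather than 18 multiplies it by 1.22 at r = 0 and 1.01 at r = 0.5.

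Both calculations treat sessions within a phase as exchangeable. If weekly position matters, they apply only to what remains after adjusting for it.

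**The case against.** The strongest reply is that one session a week is a legitimate choice. It standardises session type, and symptoms are also collected after the first treatment of the week. In the schedule as read from PDF, the later marks for blood volume and symptoms both fall in the ninth-treatment column and the weekly column is empty. That suggests a column shift, with first-of-week intended for both, so nothing here rests on the position of that mark. This reply stands as a defence of weekly sampling. It does not settle the endpoint text, which still names first and last at once.

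A reader might infer that two thirds of recorded data are thrown away. The documents do not support that. Section 7.2.2 says monitoring is performed, section 11 does not say which sessions go on study forms, and nothing says that data will be dropped. The fraction is also one third if both sessions are meant.

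A reader might also infer bias between arms. The four-week alignment argues against it: mixing sessions under a consistent rule would mainly add noise. Later selection is possible under the wording, but nothing indicates that it is planned.

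Nor are these slopes the only direct check of the refill rationale. The plasma refill test at the seventh treatment of each phase (sections 4.2.3 and 7.2.2) is a separate one, and the session wording does not touch it.

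**Conclusion.** The point holds as an under-specified endpoint with a cheap gain in precision available. The session rule can be read in more than one way, it covers 3 of 9 monitored sessions per phase (6 of 9 if both are meant), and no analysis text fixes the session or adjusts for its position in the week.

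The counts follow from the documents. The size of the gain does not: a reduction of 42% to 6% in the standard error of a phase mean rests on assumed correlations of 0 to 0.6 and does not carry over directly to the treatment contrast. The endpoints are exploratory, no power is stated for them, and the protocol calls the study a pilot. Primary and secondary conclusions are unaffected, so this is an improvement worth making and not a threat to the trial.

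**What to change.** - Define both slope endpoints in section 4.2.3 on all monitored study treatments of each phase.
- Add session of the week (first, second, third) as a fixed effect to the SAP model for these endpoints. With complete data each position occurs three times per phase, so the term is balanced against treatment; with missed sessions it protects the comparison.
- Make sections 4.2.3, 7.2.2 and 7.3.7 agree on when blood volume is monitored and when it is captured for the study, and state in section 11 which treatments the forms cover.
- If capture must stay weekly, name one fixed session of the week for all four phases before any data are examined.

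The cost is a change of wording plus more hourly values to capture and enter on study forms: up to 36 sessions per participant instead of 12. No new procedure is needed, because section 7.2.2 already has monitoring at every study treatment.

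### If treatment 7 is a blood volume slope session, the 10-minute refill test falls inside the slope window and shrinks the measured fall and the arm difference

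*Combined protocol and SAP*

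**What the plan says.** Section 4.2.3 lists two blood volume endpoints and a refill endpoint, all exploratory.

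- Endpoint 3, the hourly slope, is "measured during the 1st (last) HD treatment of each week, hour-by-hour basis".
- Endpoint 4, the by-treatment slope, runs "from start to end of HD treatment; defined as change in blood volume (%) over the entire HD treatment".
- Endpoint 5, plasma refill, is the percentage change in hematocrit over the refill test.

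Section 7.2.2 gives the procedures. "Blood volume monitoring will be performed continuously throughout each study treatment". Also, "a plasma refill test will be performed 10 minutes before HD end during the 7th treatment of each phase", and for that test "At the start of the treatment, UF time will be set 10 minutes less than treatment time". Staff note the hematocrit when UF ends and, "when the treatment ends, document the blood volume monitor hematocrit (%) again".

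Section 10.4.11 compares the slopes by ANOVA or a non-parametric method. The SAP model for continuous outcomes has a treatment term and a random intercept per participant, with no term for session number. None of these places ends the slope at UF stop, drops the last 10 minutes, or treats treatment 7 differently.

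**The concern.** At treatment 7 the last 10 minutes of the slope window are the refill test. With UF off, fluid moves back into the circulation and blood volume rises, and that rise is what endpoint 5 measures. Read literally, endpoints 3 and 4 subtract it from the UF-driven fall that they are meant to describe.

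Three things follow if treatment 7 is a slope session. Its whole-session fall is understated. Its last-hour value mixes 50 minutes of UF with 10 minutes of rebound. And it does not measure the same quantity as the other two slope sessions in the phase. The arm contrast is also affected, because the arms reach UF stop with different blood volume deficits and so rebound by different amounts.

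**Working it through.** The documents give no expected value or power for the slope endpoints, so there is no planned figure to reproduce. The check has three steps.

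**1. Is treatment 7 a slope session?** Treatments are given at "routine, scheduled outpatient thrice-weekly HD clinic visits" (section 7.1.1). A phase has 9 treatments and a wash-out has 3 (section 4.1), so each cycle is 12 treatments, or 4 weeks. Missed treatments are not made up (section 5.3). Treatment 7 therefore keeps the same weekly position in every phase. The start day is not stated.

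| Phase starts on weekly session | First-of-week treatments | Last-of-week treatments |
|---|---|---|
| 1 | 1, 4, **7** | 3, 6, 9 |
| 2 | 3, 6, 9 | 2, 5, 8 |
| 3 | 2, 5, 8 | 1, 4, **7** |

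Overlap occurs in two of the six combinations. Where it occurs, it is one slope session in three.

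**2. Simple arithmetic.** Assume a 240-minute session, a linear fall of F points by UF stop at 230 minutes, and a rebound of r points.

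- Whole session = −F + r. This reverses only if r > F.
- Last hour = −F × 50/230 + r. This reverses if r > 1.09, 2.17 or 3.26 points for F = 5, 10 or 15.
- Example with F = 10 and r = 2: the whole session reads −8 instead of −10. The last hour reads −2.17 + 2 = −0.17, against −10 × 60/240 = −2.50 with UF on to the end.

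**3. Illustrative model by arm.** From the documents: the 10-minute stop, and a profile starting at 1.33 times the constant rate. A linear fall with the same total volume then ends at 2 − 1.33 = 0.67 times. Assumed: 3 L removed, 4 h session, 5 L blood volume, and refill proportional to the deficit D with constant k = 0.5 to 2.0 per hour.

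With dD/dt = UF(t) − kD, UF time U (3.833 h at treatment 7, 4 h otherwise) and R = 3/U:

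D(t) = R × [a(1 − e^(−kt))/k − (b/U)(t/k − (1 − e^(−kt))/k²)]

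Here a = 1, b = 0 in control and a = 1.33, b = 0.66 in profiling. After UF stop, D is multiplied by e^(−k/6). The blood volume change is −100 × D/5.

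For k = 1.5 in control at treatment 7: R = 0.7826 and D(U) = 0.7826/1.5 × (1 − e^(−5.75)) = 0.520 L, or −10.4% at UF stop. Multiplying by e^(−0.25) = 0.779 gives −8.1% at the end of HD. An ordinary session gives 0.75/1.5 × (1 − e^(−6)) = 0.499 L, or −10.0%.

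Whole session, % change (losses from unrounded values):

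| k | Control: UF stop / HD end / ordinary | Profiling: UF stop / HD end / ordinary | Arm difference: ordinary → treatment 7 | Loss |
|---|---|---|---|---|
| 0.5 | −26.7 / −24.6 / −25.9 | −24.0 / −22.1 / −23.3 | 2.68 → 2.44 | 9% |
| 1.0 | −15.3 / −13.0 / −14.7 | −12.7 / −10.7 / −12.1 | 2.61 → 2.23 | 14% |
| 1.5 | −10.4 / −8.1 / −10.0 | −8.1 / −6.3 / −7.8 | 2.21 → 1.76 | 20% |
| 2.0 | −7.8 / −5.6 / −7.5 | −5.9 / −4.2 / −5.6 | 1.86 → 1.37 | 26% |

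With one of three sessions affected, the loss in the phase average is a third of this: about 3% to 9%. Reading at UF stop gives arm differences of 2.66, 2.64, 2.26 and 1.91, close to the ordinary-session values.

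Last hour, change in points:

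| k | Control: ordinary → treatment 7 | Profiling: ordinary → treatment 7 | Arm difference | Loss |
|---|---|---|---|---|
| 0.5 | −2.6 → −0.25 | +0.6 → +2.4 | 3.21 → 2.67 | 17% |
| 1.0 | −0.5 → +1.9 | +1.8 → +3.5 | 2.24 → 1.62 | 28% |
| 1.5 | −0.1 → +2.2 | +1.5 → +3.2 | 1.61 → 0.96 | 40% |
| 2.0 | 0.0 → +2.2 | +1.2 → +2.8 | 1.23 → 0.57 | 53% |

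A separate two-compartment simulation (3 L plasma, 2 L cells, 12 L interstitium, all assumed) agrees on direction. Its rebound was 1.65 to 1.85 points in control and 1.20 to 1.59 in profiling. Its whole-session arm differences fell from 2.19, 1.77 and 1.10 to 1.94, 1.41 and 0.69, a loss of 11% to 37%. Its control last-hour change shrank from between −3.9 and −3.0 to between −1.6 and −0.8, without changing sign.

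**The case against.** The strongest reply is that the overlap may not exist. If slopes fall on treatments 3, 6 and 9, or if phases start mid-week, treatment 7 is never a slope session. The schedule of events has a column headed "After 1st HD treatment of each week (3x/phase", but its layout is broken in the available text and it cannot show when slopes are taken. This stands, so the point is conditional.

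Second, the test is done in both arms, so much of the shift is common. That is true, but the shift does not cancel, because the rebound is larger in control in both models.

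Third, every magnitude rests on assumed values, the endpoints are exploratory, and monitoring is continuous, so the window could be reset at analysis. This limits the consequence. It does not remove the need to fix the window before arm data are seen.

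A reader might also infer more than the documents support:

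- *The whole-session value could reverse.* It would need the entire fall to refill in 10 minutes. In the model it is multiplied by e^(−k/6), which cannot change its sign.
- *A positive last hour is always caused by the test.* In the first model the profiled last hour is already positive without an early stop (+0.6 to +1.8), so there the sign comes from the profile.
- *The last hour is where the arms differ most.* This is not shown. The profile departs from constant UF as much at the start as at the end. In ordinary sessions the hour 1 arm difference is 1.77 points against 1.61 in the last hour at k = 1.5, and 1.44 against 1.23 at k = 2.0. The last hour leads only at lower k.
- *Dependence between endpoints 3 to 5 invalidates a test.* No joint test of them is planned.

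**Conclusion.** The point holds conditionally. As written, the slope window includes the refill test whenever treatment 7 is a slope session, and the documents do not settle whether it is. If it is, the whole-session fall is understated and the control last-hour change can turn positive (it does for k of 1.0 and above in the first model). Treatment 7 is then not comparable with the other sessions.

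Under the first model's assumptions, the whole-session arm difference at treatment 7 loses about 9% to 26% against a session without an early stop, or 3% to 9% over three sessions. These are illustrations, not bounds, since the second model gives a wider loss. Whole-session values stay negative throughout. For exploratory endpoints with at most one session in three affected, this is a minor point worth correcting because the correction is cheap.

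**What to change.** In section 4.2.3 and the SAP:

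1. State whether slopes use the first or the last session of the week, and on which weekly session phases start.
2. End both slope windows at the end of UF. At treatment 7, use the monitor reading at UF stop.
3. Keep the endpoint as a percentage change. Do not divide by UF hours, because the fall is not linear. At k = 1.5 in control, the UF-stop value differs from an ordinary session by 4% (10.40 against 9.98). Divided by UF hours the gap becomes 9% (10.40/3.833 = 2.71 against 9.98/4 = 2.50).
4. The last-hour window at treatment 7 is then 10 minutes shorter. Either compare it over the same elapsed minutes in the other sessions, or leave treatment 7 out of the last-hour value. Some difference remains under the first option: if the same volume is removed in 230 minutes, UF runs 240/230 − 1 = 4.3% faster.

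The cost is wording only. Monitoring is continuous and staff already record hematocrit at UF stop. The downside is slightly less last-hour data at one session per phase.
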